Title of trial: Comparison of Duodenal Stenting vs Transpyloric and Duodenal Stenting for Malignant Obstruction

NCT #: NCT03125148

Date of Document: March 17, 2017

STUDY PROTOCOL

Title: Comparison of Duodenal Stenting vs Trans-pyloric and Duodenal Stenting for Malignant Obstruction

Principle Investigator: [name]

Primary Contact: [name]

Purpose:

Enteral self-expanding metal stents (SEMS) are routinely used to palliate malignant gastric outlet obstruction (pancreas cancer, duodenal cancer, gastric cancer and metastasis) in patients not fit for surgical bypass. The technical success in placing these stents approaches ~100% and many of these procedures can be performed in an outpatient setting. However, the functional success (patient's ability to eat after stenting) is much lower than the technical success. One of the major reasons for this discrepancy is these patients are on narcotics which are known to be associated with poor gastric motility. At the discretion of the endoscopist, FDA approved enteral stents are placed either completely within the duodenum bridging the obstruction or placed across the pyloric opening besides bridging the duodenal obstruction.

The significance of this study is to determine if trans-pyloric extension of an intra-duodenal stent facilitates better gastric emptying compared to an intra-duodenal stent without trans-pyloric extension.

Background:

No studies have shown whether duodenal stenting by itself or duodenal stenting with transpyloric extension is superior in patients with duodenal obstruction secondary to malignancy. In one study, refractory gastroparesis secondary to benign etiologies (idiopathic, diabetes, and post-surgical) was managed with endoscopic trans-pyloric stent placement. In this study, clinical response was observed in 75% of patients. There was a predominant response in the patient's symptoms of nausea and vomiting. Gastric emptying studies were done post-stenting which showed the mean 4-hours gastric emptying normalized in 6 patients and significantly improved in 5 patients. In light of the success of trans-pyloric stenting in the setting of refractory gastroparesis due to benign pathology, we hope to show the same level of effectiveness in the setting of malignancy for which these stents are approved by FDA.

Hypothesis:

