Enteral self-expanding metal stents deployed across the malignant duodenal obstruction with trans-pyloric extension will facilitate better gastric emptying and thereby better symptom relief compared to enteral self-expanding metal stents deployed completely within the duodenum.

Aims/Objectives:

The objective of this study is to compare symptom relief and gastric emptying in the following two groups of patients with malignant gastric outlet obstruction who have enteral self-expanding metal stents deployed 1) across the malignant duodenal obstruction with trans-pyloric extension and 2) enteral self-expanding metal stents deployed completely with the duodenum without trans-pyloric extension

Recruitment Methods:

Inpatients and outpatients referred to the Gastroenterology service at Froedtert Hospital for placement of enteral stents for palliation of malignant duodenal obstruction will be recruited as per the below inclusion and exclusion criteria. These patients are generally directly referred to the advance endoscopy faculty or are referred through the GI consult service.

Inclusion Criteria

- · Confirmed diagnosis of cancer
- Evidence of a single small bowel obstruction
- Considered palliative (can be on narcotics, chemotherapy, and/or radiation therapy)
- Not a surgical candidate
- >18 years of age
- Able to give consent
- Eligible for endoscopy (medically fit)
- Able to traverse past obstruction with a guidewire

Exclusion Criteria

- <18 years of age
- Unable to give consent
- Pregnant
- Have evidence of multiple sites of obstruction in the small bowel
- Have evidence of duodenal obstruction secondary to gastric cancer
- Ineligible for endoscopy (due to comorbidities or acuity of illness)
- Unable to traverse past obstruction with a guidewire

Methods/Procedures:

This is a prospective chart review study. All the procedures are being done for clinical indications. Since patients will be randomized to group A or Group B as below, a consent form will be used.

- Prospectively enroll patients based on inclusion-exclusion criteria.
- Stent deployment completely intra-duodenal vs with trans-pyloric extension based on randomization.
- Computer-generated randomization will be conducted. We expect to randomize 20 patients each to either complete intra-duodenal stenting (Group A) or with trans-pyloric extension (Group B).

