- Symptoms of gastric outlet obstruction: heartburn, chest pain, regurgitation, bloating, belching, fullness after meals and epigastric pain will be collected from chart review prior to the procedure and post procedure as recorded during follow-up clinic visits.
- Medical record review of post-stent deployment (24-48 hrs post-deployment to allow for full expansion of the stent) gastric emptying studies.
- Solid and liquid T1/2 will be compared between these 2 groups using statistical analysis.
- An interim statistically analysis will be performed to determine if we need to study more patients.

Statistics:

We plan to study 40 patients prospectively (20 in each arm) and then using statistical software, conduct an interim analysis to determine if more patients are required. Solid and liquid T1/2 times will be compared between 2 groups using an unpaired T-test.

Risks to Participants

Patient will incur no additional risks associated with extending a stent trans-pyloric as opposed to leaving the stent completely intra-duodenal. Both these approaches are currently being practiced without any studies showing one approach being better or worse than the other. Also, patient's private and confidential information may be breached in case the data is accessed by an unauthorized person. In order to deal with this risk of confidentiality, the following measures will be taken:

- Personal identifying information will be available only to [name] and authorized study staff who are officially part of the study.
- Additionally, any paper forms will be kept in a locked cabinet at the gastroenterology department at MCW where the PI and research team members have access to the computer. The computer is password protected and only research members will have access to it. Any paper forms will be kept in a locked cabinet in the GI department.
- Once the data is complete from MCW, the data will be stored in an excel spread sheet that is password protected. The data will be stored for the duration of the study and analysis, and once the study is completed, all the de-identified data will be stored for no more than 10 years.
- Only [name] and other authorized personnel will have access to the study folder.

Consent Process

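### The t-test on T1/2 is valid but ignores narcotic use, which the protocol calls a major influence and already records; one prespecified covariate is a cheap improvement of unknown size

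*Combined protocol and SAP*

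**What the plan says.** Statistics: "Solid and liquid T1/2 times will be compared between 2 groups using an unpaired T-test". The Methods/Procedures section adds no covariate, and on allocation it says "Computer-generated randomization will be conducted", with no stratification factor. The size is given as "We plan to study 40 patients prospectively (20 in each arm"), after which the investigators will "conduct an interim analysis to determine if more patients are required".

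On narcotics, the Purpose section explains the gap between technical and functional results in these words: "One of the major reasons for this discrepancy is these patients are on narcotics which are known to be associated with poor gastric motility". The inclusion criteria allow narcotics but do not require them: "Considered palliative (can be on narcotics, chemotherapy, and/or radiation therapy"). Section E of the data form (Appendix I) asks for use (yes/no), drug name, dose and morphine equivalent. Unlike section F, which is headed as pre-procedure, section E does not say when the value is taken, nor its unit or time basis. No analysis uses these items.

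The data come from charts ("This is a prospective chart review study"), and the outcome from this source: "Medical record review of post-stent deployment (24-48 hrs post-deployment to allow for full expansion of the stent) gastric emptying studies".

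**The concern.** The protocol names a patient characteristic that it believes slows gastric motility, collects it, and then compares T1/2 without it. Any between-patient variation in T1/2 that narcotics explain stays in the error term, and with 20 per arm there is little precision to spare.

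There is also a risk of a choice made after the data are seen. Without stratification, narcotic use will differ between arms by chance. At an assumed 60% to 80% use, the SD of the between-arm difference is √(2 × 0.6 × 0.4 / 20) = 15 to √(2 × 0.8 × 0.2 / 20) = 13 percentage points. Because the protocol stresses narcotics, someone is likely to propose adjustment later, and section E offers several codings. Fixing one in advance, before the interim look, removes that freedom.

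**Working it through.** **The plan's own figure.** The 40 patients cannot be reproduced, because no alpha, power, effect size or SD is stated. Assuming two-sided 0.05 and 80% power, 20 per arm detects (1.960 + 0.842) × √(2/20) = 0.886 SD by the normal approximation, or 0.909 SD by the exact t.

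**Inputs.** From the documents: 20 per arm, randomised, unpaired t-test. Assumed: two-sided 0.05; residual SD 1; stent effect 0.83 residual SD; R² (share of within-arm T1/2 variance explained by the covariate) from 0 to 0.20; 60% to 95% of patients on narcotics; dose among users lognormal with median 60 mg and log-SD 1.0. None of these has a source in the documents.

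**Closed form, covariate in the right form.** One covariate multiplies the variance of the arm difference by (1 − R²) × 37/36, where 37/36 is the average cost of chance imbalance. Break-even on variance is R² = 1 − 36/37 = 0.027, or 0.028 once the lost degree of freedom is counted.

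For power, the t-test has noncentrality 0.83 × √10 × √(1 − R²) on 38 df: 2.625, 2.490 and 2.348 at R² 0, 0.10 and 0.20. The adjusted test has 0.83 × √10 / √(37/36) = 2.589 on 37 df at every R².

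| R² | Variance factor | CI width ratio | Equivalent unadjusted N (40 / factor) | t-test power | Adjusted power |
|---|---|---|---|---|---|
| 0 | 1.028 | 1.014 | 38.9 | 72.5% | 71.3% |
| 0.05 | 0.976 | 0.988 | 41.0 | 70.3% | 71.3% |
| 0.10 | 0.925 | 0.962 | 43.2 | 68.0% | 71.3% |
| 0.20 | 0.822 | 0.907 | 48.6 | 62.9% | 71.3% |

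The t-test column falls because the residual SD is held at 1, so narcotic variance adds to the total.

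**What these R² values mean.** For an on/off shift of g residual SD with share p on narcotics, R² = p(1 − p)g² / (1 + p(1 − p)g²). At p = 0.8, R² 0.10 needs g = √(0.111/0.16) = 0.83, as large as the assumed stent effect. R² 0.20 needs g = √(0.25/0.16) = 1.25.

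**Simulation with log(1 + morphine equivalent) as the covariate, whatever the true shape** (40,000 to 60,000 trials per setting). Power at R² 0.10, t-test then adjusted:

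| True narcotic effect | 60% use | 80% use | 90% use |
|---|---|---|---|
| On/off | 68.7 → 71.4 | 68.4 → 70.7 | 68.4 → 70.1 |
| Log-dose | 68.4 → 71.5 | 68.3 → 71.6 | 68.1 → 71.7 |
| Linear in dose | 68.5 → 69.0 | 68.5 → 69.1 | 68.4 → 69.1 |

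- At R² 0.20 and 80% use, the t-test has about 63% and the adjusted test 69% to 71% for on/off or log-dose effects, a gain of 6 to 9 points. For on/off at 90% use the gain is about 5.
- At R² 0.05 with a linear effect there is no gain.
- With an on/off shift of 0.83 SD and 95% use: 71.6% against 71.2%, a slight loss.
- With the same shift in one arm only and the average arm difference held at 0.83 SD, the change runs from about −2 to +1 points.
- Under no stent effect both tests reject in about 5% of trials (4.7% to 5.2%), so both are valid.

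**Missing dose.** If dose is missing for 20% of users, dropping them gives about 65% power at 60% use and 62% at 90%, below the t-test on all 40. Imputing the users' median, ignoring arm, with an on/off shift of 0.83 SD gives 70.7%, 70.5% and 70.8% at 60%, 80% and 90% use, against 65.8%, 68.0% and 70.1% for the t-test.

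**The case against.** The strongest reply is that nothing is broken. The t-test is valid, the benefit at R² 0.10 is worth about three patients, and 40 is not a ceiling because the interim analysis may enlarge the trial. Every input behind the gain is assumed. The sentence on narcotics concerns the ability to eat, not between-patient variance in T1/2, and if nearly all patients use narcotics a yes/no covariate explains little. Diabetes is also on the form and could be proposed instead.

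Much of this stands:
- The documents do not show that the gain is small, moderate or present at all.
- The log form is not best in every case. It gains little or nothing if the effect is linear in dose. With a linear effect at R² 0.05 and imputed doses it falls 0.4 to 0.5 points below the t-test.
- The protocol's own rationale makes unequal narcotic effects in the two arms plausible, and that removes most of the gain.
- A log(1 + dose) covariate is undefined until the unit and time basis are stated, so the fix must state them.

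What does not stand is the step from there to leaving the plan alone. The largest loss found is about 2 points. Narcotics are the one factor that the protocol itself singles out in these patients. Fixing one form in advance also prevents a data-driven choice, whatever the power gain.

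A reader might infer that the t-test is biased or confounded by narcotics. The documents do not support that: allocation is randomised, and chance imbalance is already allowed for in the test's error rate. A reader might also infer from the protocol's emphasis that the gain must be large. No prevalence, correlation or SD is given, so that does not follow either.

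**Conclusion.** The point holds as a cheap improvement, not as the correction of an error. The planned analysis leaves out a baseline variable that the protocol considers important and already collects.

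The size of the benefit cannot be derived from the documents. Under the assumed inputs it runs from a loss of 1 to 2 points of power, through nil, to gains of 2 to 4 points at R² 0.10 and 6 to 9 at R² 0.20. Those gains require an on/off or log-dose effect that is similar in both arms, and the on/off gains shrink as use becomes nearly universal. The variance factor and the break-even R² do not depend on the assumed stent effect; the power figures do. The case for acting rests on low cost, the protocol's own rationale and protection from later choice of covariate, more than on power.

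**What to change.** In Statistics, make the main analysis of solid and of liquid T1/2 a linear model on arm and one pre-procedure covariate: log(1 + total daily oral morphine equivalent in mg), with 0 for non-users. State this single form before any data are seen, including before the interim analysis. Report the adjusted difference with a 95% CI, and keep the unpaired t-test as a sensitivity analysis.

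On section E of the data form, note that the value is the last one recorded before the stent procedure and is a daily morphine equivalent in mg. A value taken after stenting could be affected by the arm and would be unsafe as a covariate. State that if the dose is missing for a known user, the median among users, ignoring arm, is imputed, so that no patient is dropped.

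The cost is a few sentences in Statistics, one note on a form that already has the items, and one degree of freedom, worth about 1 point of power if narcotics explain nothing.

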Appendix I: Data Collection Form

Data S	Sheet							
De-Ide	entified #:							
A.	Demographic	s						
	Gender: M	F	Age:	BMI:				
В.	. Primary Diagnosis causing duodenal obstruction:							
	Pancreatic Cancer Metastatic Disease			al Cancer	Lymph Nodes			
C.	Diabetes:							
	Yes	No						
D. Cancer therapy (currently/on-going):								
	Chemoth	erapy	Radiatio	on				

E.	Narcotics:						
	Yes	No	If yes: Name		Dose		
			Morphine Equ	uivalent			
F.	Pre-Procedure Symptoms (circle all that apply):						
	Heartburn	Chest Pain	Regurgitation	Bloating	Belching		
	Post-prandial	fullness	Epigastric pai	n			
G.	Stent Placem	nent:					
	Date of Proce	dure:					
	Attending:						
	Successful:		Yes	No			
	Randomizatio	n Group:	A	B			
	Full Expanded	d (within 48hrs) Yes	No			
Н.	Gastric Emptying						
	Date of Exam	:					
	Γ 1/2 (half time for gastric emptying):				% retained @1hr		
		ope of 1 st phase of emptying):			% retained @2hr		
	B2 (slope of 2	2 nd phase of em	nptying):	_	% retained @3hr		
	C (time for when slope changes from B1 to B2):				% retained @4hr		
	Overall interpretation:						
I.	Post Procedure Symptoms (circle all that apply)						
	Heartburn :	Better Same	Worse	Chest Pain:	Better Same Worse		
	Regurgitation	: Better Same	Worse	Bloating:	Better Same Worse		
	Belching:	Better Same	Worse	Post-prandial fullness : Better/same/ Worse			

Epigastric pain: Better Same Worse
